*Modified Brief Pain Inventory (BPI) – main outcome.* The BPI is a short self-assessment questionnaire that provides information on various dimensions of pain including how pain developed, the types of pain a patient experiences, and time of day pain is experienced, as well as current ways of alleviating pain [Cleeland and Ryan, 1994]. The BPI also consists of the VAS Pain scale, a simple 10-point scale (0 = “no pain”, 10 = “pain as bad as you can imagine”) measuring a patient’s worst pain and least pain, on average and at present time. The Brief Pain Inventory provides information on the intensity of pain (the sensory dimension) as well as the degree to which pain interferes with function (the reactive dimension). According to several previous studies on pain in spinal cord injury, the BPI is an effective measure [Bryce et al., 2007].

*International Spinal Cord Injury Pain Data Set.* This tool assesses average pain intensity in the last week using a 0-10 numerical rating scale. The 1-10

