7.2.3 Future analysis of genotypes: N/A

## 8.0 Study Population

### 8.1 Inclusion Criteria:

- 18 years of age or older
- Completed inpatient rehabilitation and living in the community
- Ongoing severe below-level neuropathic pain (daily average 9/10 or 10/10)
- Tried and failed to achieve adequate pain relief with the use of other drugs (previous pain management drugs failed to decrease their pain below a self-reported level of 9 out of 10)

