### *15.1 Data Analysis Plan:*

For aim 1, the main outcome variables of interest include various dimensions of pain, mood (PHQ-9), life satisfaction (SWLS), resting state brain connectivity, and community integration (CHART-SF) measured at baseline and again at 3-months of treatment. Of particular interest is whether there is a difference in pain reduction from baseline to end of study between the treatment and control groups; this will be analyzed in this pilot with linear regression including terms for group and time and the interaction of group by time. We note that many of these instruments have bounded scores and we will include analyses that recognize these (via, e.g., non- linearities or recognize the bounds such as Tobit regression) Further exploratory analyses will examine the relationships (correlations) between changes in pain and changes in mood, life satisfaction, resting state brain connectivity, and community integration using linear regression.

For aim 2, we will use the same analytic approach we have refined in our 2 active rsfMRI studies. MRI data will be analyzed using the SPM12 based Conn toolbox 3 (Version 17f, Matlab R2018b). Preprocessing steps include realignment and unwarping, slice-timing correction, ART based identification of outlier scans for scrubbing, segmentation and normalization to MNI space, and 8 mm smoothing. Denoising steps include scrubbing, aCompCor, ICA-based denoising, Global Regression, and 0.008 to 0.09 Hz band-pass filtering). Three main comparisons will be evaluated: The effect of drug treatment on rsfMRI measures, the effect of pain intensity on rsfMRI measures (each via linear regression as in Aim 1), and the differences in rsfMRI measures between active drug responders and non-responders; this last will also be analyzed via linear regression; note, however, that this will be limited to those in the active group and people in the placebo group will not be included. First, we will evaluate region-of-interest (ROI) based functional connectivity in a set of anatomically defined regions known to be impacted in SCI and neuropathic pain: the periaqueductal gray, the bilateral thalamus, the amygdala, the hippocampus, the insula, anterior cingulate, the precentral and the post-central gyrus. Second, we will evaluate, on a voxel-by-voxel basis, amplitude of low frequency fluctuations (ALFF) and intrinsic resting state functional connectivity.

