### 15.2 Power Analysis:

Part of the goal of this pilot study is to obtain information that can be used for formal sample size estimation, including effect sizes and standard error estimates; therefore, analyses are included here that may not be included in a non-pilot follow-up (including the randomization analyses described below); further, some of the analyses here are exploratory to help in the design of a follow-up study. Also, (1) robust standard errors will be used in all cases to help guard against the effects of heteroskedasticity; (2) although there are a number of outcomes and, therefore, analyses, no adjustments for multiple comparisons will be made in this pilot study as the prime aim is not the level of statistical significance but rather the estimation of results needed for planning a follow-up. Of course, when disseminating our findings we will report the number of tests performed and the actual p-values so that readers can make their own adjustments if wanted.

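### The drug effect is estimated as a difference in change without adjusting for the collected baseline value, which probably costs precision on outcomes not restricted at entry

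*Combined protocol and SAP*

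**What the plan says.** Section 15.1 lists pain, PHQ-9, SWLS, resting-state connectivity and CHART-SF as aim 1 outcomes "measured at baseline and again at 3-months of treatment". It singles out one question, "whether there is a difference in pain reduction from baseline to end of study between the treatment and control groups", and answers it with "linear regression including terms for group and time and the interaction of group by time". For aim 2, the effect of drug on the rsfMRI measures is to be analysed "each via linear regression as in Aim 1". For PHQ-9, SWLS and CHART-SF, 15.1 describes only regressions relating their changes to changes in pain. It writes no model for the drug effect on them.

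No section names the baseline value as a covariate. The other provisions do different work:
- 15.1 adds analyses for bounded scores, such as Tobit regression.
- 15.2 says that "robust standard errors will be used in all cases to help guard against the effects of heteroskedasticity". This changes how the standard error is estimated, not which contrast is estimated.
- 5.2 says that pain medication use will be recorded and considered in the analysis.
- 15.2 points ahead to randomisation analyses, but none is described.

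Section 15.2 describes the pilot's product as information for sizing the next trial, "including effect sizes and standard error estimates".

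**The concern.** A model with free terms for group, time and their interaction reproduces the four cell means. Its interaction is therefore the difference in mean change, which subtracts the whole of any baseline difference between arms. Regressing the 3-month value on arm and baseline targets the same effect under randomisation, but lets the data choose how much of the baseline difference to subtract. In large samples its variance is equal or lower.

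Two things are at stake. First, the effect estimates are noisier than they need be, and the standard errors passed to the follow-up trial are larger than the data require. Second, allocation is simple 1:1 randomisation (5.1) of a small number of people, so baseline differences will arise by chance, and part of any such difference enters the change estimate through regression to the mean. Section 15.3 compares participant characteristics between arms but states no consequence if they differ. The revision history says enrolment is complete, so precision can now come only from the analysis.

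**Working it through.** The plan gives no power, precision or correlation figure, so there is nothing of its own to reproduce.

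**Inputs.** One baseline and one 3-month value per outcome (15.1). 1:1 allocation (5.1). Total N is 40 if each of two sites enrols 20 (5.1), or 20 study-wide (23.1); both are shown. The correlation rho between baseline and 3-month values is not given and is assumed to be 0.3 to 0.8. s0 and s1 are the baseline and 3-month SDs.

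**Estimators.** With complete data:
- Planned: (difference in 3-month means) − 1 × (difference in baseline means)
- Adjusted: (difference in 3-month means) − b × (difference in baseline means), with b estimated

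**Variance per person.**
- Change: s0² + s1² − 2·rho·s0·s1
- Adjusted: s1²(1 − rho²)
- With s0 = s1, adjusted/change = (1 − rho²)/(2(1 − rho)) = (1 + rho)/2
- Estimating b multiplies the adjusted variance by about (N − 3)/(N − 4): 17/16 = 1.063 at N = 20 and 37/36 = 1.028 at N = 40

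| rho | Ratio | Variance reduction | SE reduction | Net variance reduction, N = 20 | Net variance reduction, N = 40 |
|---|---|---|---|---|---|
| 0.3 | 0.65 | 35% | 19% | 31% | 33% |
| 0.5 | 0.75 | 25% | 13% | 20% | 23% |
| 0.7 | 0.85 | 15% | 8% | 10% | 13% |
| 0.8 | 0.90 | 10% | 5% | 4% | 8% |

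Example: rho 0.5, N = 20 gives 0.75 × 1.063 = 0.797, a 20% reduction. Simulation (3,000 trials per setting) gave 31%, 22%, 9% and 4% at N = 20, and 34%, 26%, 12% and 9% at N = 40.

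**Break-even.** Setting (1 + rho)/2 × (N − 3)/(N − 4) = 1 gives rho = (N − 5)/(N − 3). This is 15/17 = 0.88 at N = 20, 35/37 = 0.95 at N = 40, and 5/7 = 0.71 at N = 10.

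**Unequal SDs.** With k = s0/s1, the share of variance saved is (rho − k)²/(1 + k² − 2·rho·k), which is zero when rho = k. Before the slope cost:
- k = 0.75: 18%, 8% and under 1% at rho 0.3, 0.5 and 0.7
- k = 1.25: 50%, 43% and 37% at the same values

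**Pain restricted at entry.** Entry requires "Ongoing severe below-level neuropathic pain (daily average 9/10 or 10/10" (8.1). The BPI asks for "worst pain and least pain, on average and at present time" (5.2). The average is confined to about 9–10, and so is the worst rating, since worst pain cannot be below average pain. Take s0 = 0.5 (a rating split evenly between 9 and 10) and an assumed s1 = 2.4.
- rho 0.2: change 0.25 + 5.76 − 0.48 = 5.53; adjusted 5.76 × 0.96 = 5.53; gain 0%
- rho 0.4: change 0.25 + 5.76 − 0.96 = 5.05; adjusted 5.76 × 0.84 = 4.84; gain 4%

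The slope cost of about 6% at N = 20 cancels this.

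**Chance imbalance.** In SD units, the baseline difference between arms has SE √(2/10) = 0.45 at 10 per arm and √(2/20) = 0.32 at 20 per arm. A difference above 0.5 SD in either direction occurs in about 26% and 11% of trials, per measure (normal approximation). With equal SDs and rho 0.5, a 0.5 SD imbalance shifts the change estimate by (0.5 − 1) × 0.5 = −0.25 SD, opposite in sign to the imbalance.

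**The case against.** The strongest reply has five parts.

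- **Scope.** The quoted model is written for pain, the outcome restricted at entry, where little or nothing is lost. This stands for BPI average and worst. The extension to rsfMRI is in the text, although the same phrase also covers a pain-intensity analysis and could mean only linear regression in general. For PHQ-9, SWLS and CHART-SF the model is an inference. PHQ-9 is also narrowed by the exclusions for suicidality and psychiatric treatment (8.2) and by removal of people who develop depression (5.2), so its SD ratio is uncertain.
- **Size.** A reader might infer that up to a third of the precision is lost. The documents do not support that figure. It is not a bound: under equal SDs one third of the variance corresponds to rho = 1/3, with more lost below that and less above. It is also a variance figure, and the SE gain at rho 0.3 is about 19%. The pain SD of 2.5 in 2.2 cannot anchor it either, because it comes from people with mean pain 3.0 and range 0–8.
- **Imaging.** Section 2.2 names periaqueductal gray ALFF as the primary imaging outcome and calls ALFF highly reliable on retest. MRI is optional and omitted for virtual participants (5.2). With an assumed 12 scanned and rho 0.8, 0.90 × 9/8 = 1.01, so the gain is gone. This stands.
- **Larger issue.** If the stacked regression is fitted without linking each person's two records, the reported SE is further off: in simulation at N = 20 and rho 0.7, 0.62 against a true 0.35. That is a separate matter. The figures above assume correct pairing.
- **Preference.** The change contrast is unbiased, answers the stated question, and can be supplemented later from the same data. This does not defeat the point. Baseline adjustment targets the same effect under randomisation, and naming it in advance avoids a choice made after seeing results.

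**Conclusion.** The point holds as a moderate efficiency issue. The plan estimates the drug effect by the difference in mean change and does not use the collected baseline as a covariate. For outcomes not restricted at entry, adjustment would lower the variance by about 35% to 10% for rho 0.3 to 0.8. Net of the slope cost this is about 31% to 4% at N = 20 and 33% to 8% at N = 40. These figures rest on assumed correlations, equal SDs and complete data. Unequal SDs can move the gain to zero or above this range.

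A reader might infer that the planned comparison is biased. It is not: over repeated randomisations it is unbiased, and the imbalance argument concerns the estimate in a particular trial. Nor do the documents support a loss on every pain rating. Among the BPI items, the argument is limited to least and present pain.

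**What to change.** In 15.1, state that for each outcome with a baseline and a 3-month value (BPI ratings, PHQ-9, SWLS, CHART-SF and region-of-interest rsfMRI summaries) the treatment effect is the arm coefficient from a regression of the 3-month value on arm and the baseline value of the same measure. Report alongside it the unadjusted difference in change and the observed baseline-to-3-month correlation, which the follow-up trial needs for its sample size. Keep the bounded-score (Tobit) analyses as planned. The voxel-by-voxel maps are outside this change. The wording should be settled before unblinding.

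The cost is plan wording and one degree of freedom (t critical value 2.101 to 2.110 at N = 20), plus about 6% (N = 20) or 3% (N = 40) added variance from estimating the slope. That can outweigh the gain when the correlation is very high and few people contribute data. Reporting the unadjusted difference beside the adjusted one makes this visible. No new data are needed.

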### 2.2 Preliminary Data:

SCI is associated with a high prevalence of severe below-level neuropathic pain that is often refractory to therapeutic interventions. Our preliminary work demonstrates overexpression of the synaptic vesicle protein 2A (SV2A) in electrically hyperactive substantia gelatinosa surgical samples in patients with neuropathic pain. The FDA-approved antiepileptic drug brivaracetam targets and binds to the SV2A protein with greater binding affinity than other drugs targeting SV2A. We have used brivaracetam off-label for compassionate reasons in severe, refractory neuropathic pain with sustained pain relief. We have identified multiple brain networks altered in SCI and modulated by neuropathic pain. Neuropathic pain also increases local brain activity of the periaqueductal gray. miR-485 regulates presynaptic expression of SV2A as well as dendritic spine density and synapse morphology and function. Therefore, circulating miR-485 may be a mechanism-based predictive biomarker of response to therapies targeting the SV2A protein, including brivaracetam. These findings, paired with our preliminary data, suggest that reduced levels of miR-485 may contribute to the pathophysiology of SCI-induced neuropathic pain by disrupting normal levels of SV2A and neural network activity in nociceptive neurons. Collectively, these findings provide the scientific rationale for the following hypotheses to be tested in this pilot clinical trial: compared to placebo, treatment with brivaracetam reduces severe below-level SCI neuropathic pain with corresponding reduction in periaqueductal gray brain activity by rsfMRI (Aim 1). We also hypothesize that either periaqueductal gray brain activity or circulating miRNA-485 may be candidate predictive biomarkers of response to brivaracetam therapy. Collectively, the results of this pilot clinical trial will be used to design larger clinical trials to confirm these hypotheses.

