## 5.0 Procedures Involved

### 5.1 Study Design:

This is a multi-center randomized, double-blinded placebo-controlled pilot clinical trial. Each site (Swedish Medical Center/Craig Hospital, UMN) will enroll and study 20 adults, 18 years of age and older with SCI. [name] will serve as PI, and [name] will serve as Co-I at UMN (local site). MRI data analysis will be conducted by [name] (Harvard University). [name] will receive a deidentified dataset and will have no human subject interactions. Research activities at the Swedish Medical Center/Craig Hospital will be conducted under a separate IRB protocol at Craig Hospital.

Participants who meet the eligibility criteria will be randomly assigned to active drug (escalating brivaracetam dose to 100 mg twice daily for 3 months) or placebo based on a randomization schedule developed by our biostatistician. This is a simple computer generated 1:1 scheme that randomly assigns participants to arm A or arm B. Study participants, research coordinators, and study personnel involved in outcomes assessments and analyses will all be blinded. The drug will be provided by RxArtisans pharmacy in Wayzata, MN. The active and placebo capsules will have identical appearance and consistency. Treatment assignment will be known only to the investigational drug pharmacies (RxArtisans). We have registered this pilot study with National Institutes of Health (NIH) clinical trials registry, [www.clinicaltrials.gov](http://www.clinicaltrials.gov) (NCT04379011). The pilot data generated by this effort will be used to power a subsequent multi-center clinical trial.

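### Section 15.1 specifies no treatment-arm term for the exploratory change-on-change regressions, so a drug effect on both measures could create, or mask, an apparent link between them

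*Combined protocol and SAP*

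**What the plan says.** Section 15.1 (Data Analysis Plan) describes four analyses that bear on this point.

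- **Main pain comparison, Aim 1.** The model is "linear regression including terms for group and time and the interaction of group by time".
- **Exploratory relationships, Aim 1.** Two sentences later, the plan turns to exploratory work intended to "examine the relationships (correlations) between changes in pain and changes in mood, life satisfaction, resting state brain connectivity, and community integration using linear regression". No arm term, stratification by arm or other covariate is named.
- **Pain intensity and rsfMRI, Aim 2.** One comparison is "the effect of pain intensity on rsfMRI measures (each via linear regression as in Aim 1", so this one carries a reference back to the Aim 1 model.
- **Responders and non-responders on rsfMRI, Aim 2.** The plan says that "this will be limited to those in the active group and people in the placebo group will not be included".

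Section 2.2 gives the hypothesis that, compared with placebo, "treatment with brivaracetam reduces severe below-level SCI neuropathic pain with corresponding reduction in periaqueductal gray brain activity by rsfMRI". Section 15.2 says that robust standard errors will be used throughout, that some analyses are exploratory, and that the prime aim is estimation for planning a follow-up rather than statistical significance.

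**The concern.** A regression of one change score on another, fitted to both arms without arm in the model, answers two questions at once. One is whether people with more pain relief also have more change in mood or brain activity. The other is whether the two arms differ on both measures. If the drug moves both, the arms form two clusters, and the line through them has a slope even when neither cluster has one.

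For pain and periaqueductal gray activity, a drug effect on both is what the trial hypothesises. For mood it is only a possibility: Section 13.1 lists depression and irritability among the drug's risks, so mood could shift by its own route and in the unfavourable direction. The documents give no separate drug route for life satisfaction or community integration.

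At stake is the interpretation of the pilot. A pooled correlation could be taken as evidence that brain change accompanies pain relief in individuals, or that pain relief lifts mood, when it reflects randomised treatment acting on each. Sections 1.1 and 15.2 say that the pilot's estimates will be used to design the next trial.

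**Working it through.** **Inputs from the documents**

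- Allocation, Section 5.1: "This is a simple computer generated 1:1 scheme that randomly assigns participants to arm A or arm B".
- Total N: Section 23.1 gives 20 study-wide, while Section 5.1 gives 20 at each of two sites, which makes 40. Both are used.
- Significance level, Section 15.3: 5%. Sidedness is not stated; two-sided is assumed.
- Standard errors, Section 15.2: robust, with the variant not named.

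The documents give no effect size, SD or correlation for these analyses, so there is no planned figure to reproduce. The arm shifts below are assumptions, expressed in within-arm SDs.

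**Closed form.** Let the drug shift the two change scores by d1 and d2, with unit within-arm SDs and no within-arm association. With half the participants in each arm, the between-arm covariance is d1·d2/4, and the variances are 1 + d1²/4 and 1 + d2²/4. Hence

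pooled r = (d1·d2/4) / √[(1 + d1²/4)(1 + d2²/4)].

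With d1 = d2 = d this is (d²/4)/(1 + d²/4):

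- d = 0.5: 0.0625/1.0625 = 0.06
- d = 0.8: 0.16/1.16 = 0.14
- d = 1.0: 0.25/1.25 = 0.20
- d = 1.5: 0.5625/1.5625 = 0.36

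If only one measure shifts, d1·d2 = 0 and pooled r = 0.

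**Rejection rates.** 40,000 simulated trials per setting, equal arms, normal data, two-sided 5% t-test of the slope, true within-arm correlation 0:

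| Shift on both (SD) | N=20, no arm term | N=40, no arm term | With arm term, either N |
|---|---|---|---|
| 0 | 4.9% | 4.9% | 4.9% |
| 0.5 | 5.6% | 6.5% | 4.9% to 5.1% |
| 0.8 | 9.0% | 13.7% | 4.9% |
| 1.0 | 13.8% | 24.0% | 5.0% |
| 1.5 | 37.4% | 67.1% | 4.9% to 5.1% |

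With a shift of 0.8 SD on one measure and none on the other, the rate without an arm term is 5.0% at N=20 and 5.1% at N=40.

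**Robust standard errors** (3,000 trials per setting). With HC3 and 1.0 SD on both measures, the rates without an arm term are 13.5% at N=20 and 25.3% at N=40. With an arm term, HC3 gives 4.1% to 5.1% over all settings. HC1 runs high at these sizes even with no shift and no arm term (7.7% at N=20, 6.7% at N=40). That is a separate small-sample matter which an arm term does not cure. Neither variant removes the effect of leaving arm out.

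**Masking.** Take shifts of +1 and −1 SD. The between-arm covariance is (1)(−1)/4 = −0.25. A true within-arm correlation of 0.25 then gives a pooled covariance of 0.25 − 0.25 = 0.

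**Sensitivity.** Randomisation is simple, so the arms may be unequal. With proportion p in one arm, 1/4 becomes p(1 − p). A 12:8 split gives 0.6 × 0.4 = 0.24, and at d = 1 the pooled r is 0.24/1.24 = 0.19 instead of 0.20. For connectivity the sample is smaller than the total N, because MRI is optional and virtual participants are not scanned (Section 5.2). The closed-form r does not depend on N, while the rejection rates fall as N falls.

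**The case against.** The strongest reply has four parts.

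**Silence is not a decision.** A reader might infer that the plan has chosen to pool the arms. It has not said so; it lists no covariates for these models and does not rule arm out. That stands, and the point is only that no arm term is specified. Even so, the same section names group terms and an arm restriction where it wants them, so someone following the text literally would fit the pooled model.

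**Aim 2 covers the brain measures.** A reader might infer that these regressions are the only planned look at whether brain change tracks pain change. They are not. Aim 2 also relates pain intensity to rsfMRI, and it compares responders with non-responders inside the active arm, which a gap between arms cannot produce. Nor does the text support saying that the Aim 2 pain-intensity regression lacks arm: its reference to Aim 1 can be read as bringing in the group term. For mood, life satisfaction and community integration, no other analysis relating their change to pain change is described.

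**The pooled correlation is a legitimate quantity.** If the drug moves both measures, the marginal correlation is truly non-zero, and rejecting zero is no error for that quantity. This is fair, and it is a reason to report both. The rates above count as false positives only when the result is read as an association within arms, which is the natural reading when relating individual changes. If pain relief does go with mood or brain change in individuals, the arm-adjusted slope still shows it.

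**The analyses are exploratory, in a pilot.** True, and this limits severity. However, the problem is in the estimate and not only in the p-value, and estimation is the pilot's stated aim. Reporting exact p-values and the number of tests does not correct it.

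**Conclusion.** The concern holds as a gap in specification. Followed literally, the change-on-change regressions would mix between-arm and within-arm association. The size is conditional: nil when only one measure shifts and there is no within-arm link, negligible at 0.5 SD on both, and material from about 0.8 to 1.0 SD on both. The chance of a misleading significant result grows with N, so the habit would cost more in the larger trial.

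These figures rest on assumed shifts, normal data, equal arms and zero within-arm correlation. The condition of an effect on both measures is hypothesised only for pain and periaqueductal gray activity; for mood it is merely possible.

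A reader might infer that the trial's efficacy conclusion is compromised. The documents do not support that: the group-by-time comparison of pain already includes arm, and neither primary endpoint in Section 3.1 depends on these regressions. This is a low-to-moderate-severity improvement to an exploratory analysis.

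**What to change.** In Section 15.1, add after the sentence on exploratory relationships:

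> Each change-on-change regression includes treatment arm as a covariate. The arm-adjusted slope with its 95% CI is reported alongside the pooled correlation, and arm-specific slopes are shown descriptively.

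For the Aim 2 regression of rsfMRI measures on pain intensity, only confirm that the reference to Aim 1 includes the group term.

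The cost is one degree of freedom per model (residual degrees of freedom go from 18 to 17 at N=20, and from 38 to 37 at N=40) and no new data. The revision history records enrolment as complete, which does not matter for this change; it is best fixed before unblinding.

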### 1.0 Objectives

#### 1.1 Purpose:

SCI is associated with severe neuropathic pain that is often refractory to all pharmacological intervention. Our preliminary data suggest brivaracetam is a mechanism-based pharmacological intervention for neuropathic pain in SCI. In this project we will conduct a randomized, placebo-controlled pilot clinical trial to assess feasibility of a 3-month treatment course with brivaracetam. We will assess changes in pain intensity and periaqueductal gray hyperactivity. We will assess baseline periaqueductal gray hyperactivity and microRNA levels as potential biomarkers of response to treatment. We will use these preliminary findings to design larger clinical trials to establish efficacy of brivaracetam to treat neuropathic pain in SCI. The pilot data are necessary to adequately power the larger clinical trial based on SCI-specific data for each outcome of interest. Here we will be able to present the scientific evidence base supporting the rationale for this project.

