### **3.0 Study Endpoints/Events/Outcomes**

#### **3.1 Primary Endpoint/Event/Outcome:**

Our primary endpoints will be 1) safety as determined by number of drug related adverse events and assessed through weekly adverse event screening by phone, and 2) efficacy as determined by reduction in pain intensity assessed by the Brief Pain Inventory. We will use the clinically meaningful reduction in Brief Pain Inventory score of 1 point or more as the definition of “drug response” in this study.

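### Baseline PAG activity is named a candidate predictor of brivaracetam response, but the only rsfMRI response analysis leaves out placebo, so a merely prognostic marker could be reported as predictive

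*Combined protocol and SAP*

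**What the plan says.** Section 1.1 (Purpose): "We will assess baseline periaqueductal gray hyperactivity and microRNA levels as potential biomarkers of response to treatment". Section 2.2 (Preliminary Data) hypothesises that "either periaqueductal gray brain activity or circulating miRNA-485 may be candidate predictive biomarkers of response to brivaracetam therapy".

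Section 15.1 lists three Aim 2 comparisons. The first two are the effect of treatment on rsfMRI measures and the effect of pain intensity on rsfMRI measures, both by the Aim 1 regression approach. The third is "the differences in rsfMRI measures between active drug responders and non-responders; this last will also be analyzed via linear regression", and it is "limited to those in the active group and people in the placebo group will not be included". Section 3.1 takes a "clinically meaningful reduction in Brief Pain Inventory score of 1 point or more as the definition of" drug response.

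The Aim 1 model is "linear regression including terms for group and time and the interaction of group by time". The Aim 1 exploratory analyses relate "changes in pain and changes in mood, life satisfaction, resting state brain connectivity, and community integration using linear regression". Aim 3 deals with microRNA only.

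**The concern.** A marker is predictive of benefit from a drug when its relation to outcome differs between drug and control. A marker that tracks outcome equally in both arms is prognostic: it says who improves, whatever they are given. An analysis confined to the active arm sees one slope and cannot tell the two apart. A larger active arm, a better response cut or a continuous outcome would not help, because the missing quantity is the slope on placebo.

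The prognostic explanation is plausible here. Section 8.1 requires daily average pain of 9 or 10 out of 10, so some regression to the mean is likely in both arms, and a 1-point fall counts as response. Section 2.2 reports a positive correlation between pain rating and PAG ALFF, so baseline PAG could relate to later pain change with no drug involved.

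At stake is what the pilot passes on. Its purpose is to inform larger trials, and section 2.1 expects those trials to validate predictive biomarkers. An active-only association would hand them the wrong quantity, although placebo participants who consent to MRI are scanned on the same schedule.

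**Working it through.** **Step 1. Does any planned analysis supply the placebo comparison?** Taking each section 15.1 analysis in turn:

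- Aim 1 model: group, time and group by time. It has no baseline marker and no marker-by-group term.
- Aim 1 exploratory analyses: changes against changes, not a baseline marker against response.
- Aim 2, treatment effect on rsfMRI: uses both arms, but asks whether the drug alters the scan, not whether the baseline scan forecasts pain response.
- Aim 2, pain intensity and rsfMRI: does not relate baseline PAG to response by arm.
- Aim 2, responders against non-responders: concerns response, but on active only, and the scan (baseline, follow-up or change) is not named.
- Aim 3: microRNA.

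No baseline-PAG-by-arm term is planned, nor a parallel placebo estimate.

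**Step 2. How often could a purely prognostic marker be flagged?** The plan gives no effect size, SD or power for this analysis, so there is no figure to reproduce. The size was illustrated by simulation, 6,000 runs per setting.

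Inputs from the documents: 1:1 allocation (5.1); 5% level (15.3), taken as two-sided; robust standard errors (15.2); response at a fall of 1 point or more (3.1). Section 23.1 gives 20 participants study-wide and section 5.1 gives 20 per site, 40 in all, so both 10 and 20 active participants were run.

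Assumed, not in the documents: marker SD 1; SD of pain reduction 2; mean reduction 1 on placebo and 2 on active; correlation rho between marker and pain reduction, the same in both arms.

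Model: reduction = 1 + 1 × arm + 2 × (rho × marker + √(1 − rho²) × noise).

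The planned type of test regresses the marker on responder status in the active arm. The alternative regresses reduction on arm, marker and arm × marker in both arms and tests the interaction. Because the slopes are equal, every significant result read as prediction is a wrong reading.

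| Active n | rho | Active-only, ordinary SE | Active-only, HC3 robust SE | Interaction, ordinary SE | Interaction, HC3 |
|---|---|---|---|---|---|
| 10 | 0.3 | 10.5% | 10.0% | 4.8% | 3.4% |
| 10 | 0.5 | 21.6% | 19.0% | 5.2% | 3.4% |
| 10 | 0.7 | 41.2% | 36.6% | 4.9% | 3.3% |
| 20 | 0.3 | 16.4% | 15.8% | 4.7% | 4.5% |
| 20 | 0.5 | 40.0% | 36.8% | 4.8% | 4.2% |
| 20 | 0.7 | 74.4% | 71.4% | 5.1% | 4.1% |

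Active-only rates are among runs with at least two responders and two non-responders (about 86–87% of runs at 10 active, 99% at 20). Repeat runs agreed within about a percentage point, apart from the 10-active, rho 0.5 cell, where one gave about 19% with ordinary errors; the lowest cell fell to about 9%. With no drug effect at all and rho 0.5, the active-only test (ordinary SE) is still significant in 20.5% (10 active) and 43.5% (20 active). The rate rises with sample size because the association is real; only its interpretation is wrong.

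**Step 3. What can the interaction deliver at this size?** With residual SD 2 and marker SD 1, the SE of the slope difference is 2 × √(2/n per arm).

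- 10 per arm: 2 × √0.2 = 0.89 points per marker SD. Detectable with 80% power: 0.89 × (1.96 + 0.84) ≈ 2.5.
- 20 per arm: 2 × √0.1 = 0.63. Detectable: 0.63 × 2.80 ≈ 1.8.

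A marker with r = 0.5 on active and 0 on placebo has a slope difference of 0.5 × 2 = 1 point per SD, far below both. Simulated power with ordinary standard errors is about 18% at 10 per arm and 34% at 20 per arm.

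**The case against.** The strongest reply is that the responder comparison may not be the biomarker analysis at all. Section 1.1 states Aim 2 as whether the drug lowers PAG activity, and only Aim 3 is a baseline-marker aim. Section 15.1 mentions neither baseline nor prediction for this comparison. It could be a mechanistic look at follow-up or change scans, where staying within the active arm is less objectionable. This stands in part: a reader might infer that the plan designates the active-only comparison as its test of prediction, and the documents do not say so. But then sections 1.1 and 2.2 promise an assessment of baseline PAG that section 15.1 nowhere specifies, so the gap remains.

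Second, the language is tentative (potential, candidate, may be), confirmation is left to larger trials, and section 15.2 puts estimation ahead of significance. That lowers the weight of any 5% criterion. It does not remove the point, because a planning pilot still has to estimate the right quantity.

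Third, no data in the documents support a particular correlation between baseline PAG and pain change, so the percentages are illustrative. This stands, and is why a range of rho is shown.

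Fourth, the interaction has little power here. That also stands. A reader might infer that the placebo scans would answer the predictive question; at 10 to 20 per arm they would not.

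**Conclusion.** The concern holds in a limited form. The plan commits to assessing baseline PAG as a candidate predictor of brivaracetam response. Its one rsfMRI response analysis excludes placebo and leaves the scan time unstated, and nothing else fills the gap. A prognostic marker could therefore be reported as predictive. The chance is roughly 10–40% with 10 active participants and 16–74% with 20, for rho from 0.3 to 0.7, conditional on the assumed SD and mean reductions and on the baseline scan being the one used.

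Stronger readings are not supported. A prognostic marker would not necessarily pass: with 10 active and rho 0.5, about four trials in five would not flag it. Nothing says that the next trial will select patients on PAG. Aim 2 as stated, the effect of treatment on PAG activity, is analysed in both arms and is not affected.

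This should be corrected, at the weight of a secondary, exploratory question.

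**What to change.** Add to section 15.1:

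> Baseline PAG ALFF as a candidate predictor is assessed in all randomised participants with a baseline scan by regressing BPI change on arm, baseline PAG ALFF and their interaction, with robust standard errors; the interaction estimate and 95% CI are reported as a planning estimate. The active-only responder comparison is descriptive and will not be called predictive.

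The text should also state which scan the responder comparison uses, and name the robust standard error; HC3 kept the interaction test at or below 5% in the settings checked.

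The cost is one model on data already scheduled for collection. The revision history records enrolment as complete, but analysis text can still be amended, preferably before unblinding. The downside is a wide interval. Power is about 18% at 10 per arm and 34% at 20 per arm if r is 0.5 on active and 0 on placebo. It will be lower in practice, because MRI is optional and virtual participants are not scanned (section 5.2), and HC3 is somewhat conservative. The result informs the design of the next trial and should be presented that way.
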